8.2 ENDPOINTS

8.2.1 Primary endpoint

The primary endpoint is the evaluation of response rate (CR and PR) at 6 months after the first ATO infusion, with no secondary systemic therapy at any time before M6.

NIH grade of chronic GVHD will be used for the exact definition of this endpoint.

- Complete remission (CR) is defined as complete disappearance of any sign of chronic GvHD
- Partial remission (PR) is defined as improvement of 1 or more point on a 4 to 7-points scale or an improvement of 2 or more points on a 10 to 12-points scale in at least 1 organ or site without progression in any other organ or site.
- More details for response determination are given in the following table:

Organ	Complete Response	Partial Response	Progression
Skin	NIH Skin Score 0 after previous involvement	Decrease in NIH Skin Score by 1 or more points	Increase in NIH Skin Score by 1 or more points, except 0 to 1
Eyes	NIH Eye Score 0 after previous involvement	Decrease in NIH Eye Score by 1 or more points	Increase in NIH Eye Score by 1 or more points, except 0 to 1
Mouth	NIH Modified OMRS 0 after previous involvement	Decrease in NIH Modified OMRS of 2 or more points	Increase in NIH Modified OMRS of 2 or more points
Esophagus	NIH Esophagus Score 0 after previous involvement	Decrease in NIH Esophagus Score by 1 or more points	Increase in NIH Esophagus Score by 1 or more points, except 0 to 1
Upper GI	NIH Upper GI Score 0 after previous involvement	Decrease in NIH Upper GI Score by 1 or more points	Increase in NIH Upper GI Score by 1 or more points, except 0 to 1
Lower GI	NIH Lower GI Score 0 after previous involvement	Decrease in NIH Lower GI Score by 1 or more points	Increase in NIH Lower GI Score by 1 or more points, except from 0 to 1
Liver	Normal ALT, alkaline phosphatase, and Total bilirubin after previous elevation of 1 or more	Decrease by 50%	Increase by 2 × ULN
Lungs	- Normal %FEV1 after previous involvement - If PFTs not available, NIH Lung Symptom Score 0 after previous involvement	- Increase by 10% predicted absolute value of %FEV1 - If PFTs not available, decrease in NIH Lung Symptom Score by 1 or more points	- Decrease by 10% predicted absolute value of %FEV1 - If PFTs not available, increase in NIH Lung Symptom Score by 1 or more points, except 0 to 1

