17. APPENDICES

17.1 RESPONSE CALCULATION ALGORITHM

Etude GMED_16_001 : Evaluation des réponses complètes et partielles – 19/10/2020

Les réponses sont définies comme (règles de calcul basées sur le protocole et l'article Lee et al)

- Complete response at a visit: Lorsque tous les scores de « cGVHD activity assessment form A » des organes suivants sont à 0 ou que la variable "abnormalities present but explained entirely by non-GVHD documented cause » soit égale à Oui.

Détails :

Si une valeur est manquante pour un des organes atteints lors de la visite V1, la réponse ne peut pas être considérée comme complète. le fait que la valeur est manquante sera documentée.

Si une valeur à la visite d'intérêt est manquante sur un organe non atteint lors de la visite V1, la réponse complète peut être établie, car les réponses complètes ou partielles ne sont établies que sur les organes atteints à V1.

Si « abnormalities present but explained entirely by non-GVHD documented cause » = Oui pour un organe à la visite considérée, le score de cet organe n'est pas corrigé et cet organe n'est pas considéré pour l'évaluation de la réponse complète. cela ne créera pas de valeur manquante pour cet organe et n'empêchera pas la réponse d'être considérée comme complète si les informations sur les autres organes sont disponibles.

- BSA=0 ET skin features=0

M6_GVHD_A_S (préfixe M6 ou C1W6, W14, M9 et M12 selon la visite considérée)

M6_GVHD_A_S_F_S

M6_GVHD_A_S_ABN

- Eyes=0

M6_GVHD_A_E

M6_GVHD_A_E_ABN

- Gastrointestinal=0 (pour chacun des 3 scores : Gastro-oesophageal, Gastro-upper, Gastro-lower)

M6_GVHD_A_GASTRO1

M6_GVHD_A_GASTRO2

M6_GVHD_A_GASTRO3

M6_GVHD_GAST_ABN

- Mouth=0 (considérer la somme des 3 scores : Erythema, Lichenoid, Ulcers)

M6_GVHD_A_MOUTH1
 M6_GVHD_A_MOUTH2
 M6_GVHD_A_MOUTH3
 M6_GVHD_MTH_ABN

Joint and fascia =0

M6_GVHD_A_J
 M6_GVHD_A_J_ABN

Liver : les 3 valeurs (Bilirubine, ALAT et PAL) sont en dessous des ULN (Unité limite supérieure) si le score hépatique était >0 à V1 (table 1 et annexe du protocole)

.<M6_GVHD_A_L_SGPT_V<=M6_GVHD_A_L_SGPT_U_V
 .<M6_GVHD_A_L_ALK_V<=M6_GVHD_A_L_ALK_U_V
 M6_GVHD_LIV_ABN

Le score à V1 est calculé comme :

Score = 0 : Bilirubine normale WITH ALAT AND PAL < 3 UNL

(.<V1_GVHD_A_L_BILI_V<=V1_GVHD_A_L_BILI_U_V et
 .<V1_GVHD_A_L_SGPT_V<3* V1_GVHD_A_L_SGPT_U_V et
 .<V1_GVHD_A_L_ALK_V<3* V1_GVHD_A_L_ALK_U_V)

Score = 1 : Bilirubine normale WITH 3 UNL<=ALAT < 5 UNL AND 3 UNL <=PAL<5 UNL

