Score = 2 : Bilirubine élevée (>1*ULN) mais <= à 3 mg/dL OR ALAT >= 5 UNL OR PAL >=5 UNL (non mentionné dans article NIH).

Score = 3 : Bilirubine élevée > à 3 mg/dL

Lung : si FEV1 >=80% et FEV1<70 à V1. et dans le cas où la valeur de FEV1 est manquante, si le score est égal à 0

M6_GVHD_A_LU_FEV1_V>= 80
 missing(M6_GVHD_A_LU_FEV1_V) and M6_GVHD_A_L=0
 M6_GVHD_A_L
 M6_GVHD_A_L_ABN

Calcul de réponse par organe :

Aucun calcul de réponse **par organe** (complète, partielle ou progression) n'est effectué si :

- « abnormalities present but explained entirely by non-GVHD documented cause » = Oui pour un organe à la visite considérée
- CR_*organe*, PR_*organe* et PD_*organe* sont alors mis à . (manquant)

Aucun calcul de réponse complète ou partielle **par organe** n'est effectué si :

- l'organe n'est pas atteint à V1 ou abnormalities present but explained entirely by non-GVHD documented cause » = Oui pour un organe à la visite V1.
- la progression est recherchée même si pas d'atteinte à V1
- CR_*organe* et PR_*organe* sont alors mis à . (manquant)

- **Partial response by organ:** en se basant sur les mêmes scores et en s'intéressant aux diminutions (ou augmentations) entre V1 (mêmes variables qu'indiquées précédemment mais qui commencent par « V1 » au lieu de « M6 ») et la visite considérée (M6, W6, W14, M9 ou M12)

- une diminution d'1 point pour les scores sur des échelles de 0 à 4 pour : Skin BSA, Skin features, Eyes, Joints, Gastro-oesophageal, Gastro-upper, Gastro-lower,
- une diminution de 2 points pour la somme des 3 sous-scores pour Mouth
- pour Lung, une augmentation entre V1 et la visite d'au moins 10% sur FEV1 avec FEV1 à V1 <70. Dans le cas de FEV1 manquants à V1 et ou M6, une diminution d'1 point sur le score 'lungs'
- pour Liver, (Bilirubine, ALAT ou PAL),
- si les valeurs à M6 sont en dessous des normales, la réponse est considérée Complète
- sinon la recherche d'une réponse partielle est effectuée : diminution de 50% de la valeur initiale
 Le ratio est calculé ainsi : $(M6-V1/V1)*100$ et si le ratio est inférieur à -50 (mais pas de progression pour une des autres valeurs), il y a une réponse partielle

Global Partial response: au moins une réponse partielle sur un organe et avec une absence de progression pour un autre site

- **Progressive disease by organ:**

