- peau, yeux, œsophage, tractus gastro-intestinal supérieur et inférieur : augmentation 1 point ou plus sur échelle de 0 à 3 = progression SAUF si changement de 0 à 1 (progression non spécifique)
- Joint: augmentation d'1 point ou plus = progression
- bouche : changement de 2 points ou plus sur la somme des 3 sous-scores

- pour Lung, diminution de 10 % avec FEV1 à V1 < 75% . Dans le cas de FEV1 manquants, augmentation d'1 point ou plus *SAUF* si changement de 0 à 1 (progression non spécifique)

- pour Liver, si l'une des valeurs à M6 est au-dessus de la normale pour Bilirubine, ALAT ou PAL, la recherche d'une progression est effectuée : la différence M6 – V1 est calculée et si la différence est supérieure à 2*ULN, il y a Progression.

Global progressive disease : si au moins un site avec une progression

Mixed response: si **Progressive disease** sur au moins un organe et **Partial response** sur au moins un autre

Extraits du protocole :

Table 4. Response determination for chronic GvHD (extrait du protocole)

Organ	Complete Response	Partial Response	Progression
Skin	NIH Skin Score 0 after previous involvement	Decrease in NIH Skin Score by 1 or more points	Increase in NIH Skin Score by 1 or more points, except 0 to 1
Eyes	NIH Eye Score 0 after previous involvement	Decrease in NIH Eye Score by 1 or more points	Increase in NIH Eye Score by 1 or more points, except 0 to 1
Mouth	NIH Modified OMRS 0 after previous involvement	Decrease in NIH Modified OMRS of 2 or more points	Increase in NIH Modified OMRS of 2 or more points
Esophagus	NIH Esophagus Score 0 after previous involvement	Decrease in NIH Esophagus Score by 1 or more points	Increase in NIH Esophagus Score by 1 or more points, except 0 to 1
Upper GI	NIH Upper GI Score 0 after previous involvement	Decrease in NIH Upper GI Score by 1 or more points	Increase in NIH Upper GI Score by 1 or more points, except 0 to 1
Lower GI	NIH Lower GI Score 0 after previous involvement	Decrease in NIH Lower GI Score by 1 or more points	Increase in NIH Lower GI Score by 1 or more points, except from 0 to 1
Liver	Normal ALT, alkaline phosphatase, and Total bilirubin after previous elevation of 1 or more	Decrease by 50%	Increase by 2 × ULN

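### The computed complete-response rule in SAP 17.1 does not test livers uninvolved at V1 and does not rank complete response against progression, so new liver GvHD at M6 can be filed as complete response

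*SAP*

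**What the plan says.** SAP 8.2.1 states the target: "Complete remission (CR) is defined as complete disappearance of any sign of chronic GvHD". SAP 17.1 turns this into a programmed response.

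- **CR header.** CR holds "Lorsque tous les scores de « cGVHD activity assessment form A » des organes suivants sont à 0", or when the abnormality is attributed to a documented non-GvHD cause.
- **CR by organ.** The skin, eye, gastrointestinal, mouth and joint lines ask for 0 at the visit, with no condition on V1. For the liver, bilirubin, ALT and alkaline phosphatase (AP) "sont en dessous des ULN (Unité limite supérieure) si le score hépatique était >0 à V1".
- **Scope.** On missing values, the appendix explains that a gap in an organ uninvolved at V1 does not block CR, "car les réponses complètes ou partielles ne sont établies que sur les organes atteints à V1".
- **Global PR** needs "au moins une réponse partielle sur un organe et avec une absence de progression pour un autre site". Global CR has no equivalent clause.
- **Progression.** For organs uninvolved at V1, "la progression est recherchée même si pas d'atteinte à V1". For the liver, the M6 minus V1 difference is taken and "si la différence est supérieure à 2*ULN, il y a Progression". Then: "Global progressive disease : si au moins un site avec une progression".
- **Mixed response** is progression in one organ with PR in another. Protocol 9.3 defines it as CR or PR in one organ with progression in another.

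The computed response is used in SAP 11.4.1.2, sensitivity analyses b and d. SAP 11.4.2.2 b takes global PD from 17.1 as the PFS event.

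**The concern.** A liver scored 0 at V1 faces no test under CR at M6. New liver disease there cannot block CR, although new disease in the skin, eyes, gut, mouth or joints would. The only other safeguard is progression, and 17.1 attaches that to PR alone.

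The main analysis is the investigator's own judgement in an unblinded single-arm trial, and the computed response is the rule-based check on it. If the rule calls a patient a complete responder while a new organ is affected, the check departs from the SAP's own definition of CR. Where the rise is large, one patient can be a responder in Table 14.2.2.3 and a progression event in Table 14.3.2.3a.

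**Working it through.** The plan states no figure for this point, so the check applies the rules to test patients.

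**Inputs.** CR, PD and liver rules from SAP 17.1; liver score at the visit from the derivation table in SAP 11.2.3. The documents give no bilirubin ULN, so I assumed 1.0, 1.2 and 1.3 mg/dL, which makes 2 x ULN equal to 2.0, 2.4 and 2.6 mg/dL. Results were the same for all three. In the first four rows the V1 liver score is 0, every other organ is 0 at M6, the non-GvHD flag is not set, and liver values not shown are normal.

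| Liver, V1 to M6 | Rise | Score at M6 | CR | Global PD |
|---|---|---|---|---|
| ALT 1 to 3 x ULN | 2 x ULN, not above the limit | 1 | yes | no |
| Bilirubin 0.6 to 2.5 mg/dL | 1.9 mg/dL, below 2.0 to 2.6 | 2 | yes | no |
| ALT 1 to 6 x ULN | 5 x ULN | 2 | yes | yes |
| Bilirubin 0.6 to 5 mg/dL | 4.4 mg/dL, above 2.0 to 2.6 | 3 | yes | yes |
| Control: ALT 6 x ULN at both visits (V1 score 2) | 0 | 2 | no | no |
| Control: ALT 1 to 6 x ULN, another organ not 0 | 5 x ULN | 2 | no | yes |

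**Where each patient belongs.** Suppose the cleared organ was skin, 2 at V1 and 0 at M6.

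- *Large rise:* a mixed response under Protocol 9.3, so not a responder. CR+PR is overstated by one if the CR flag is used.
- *Small rise:* not CR, because liver involvement is present, but still PR, because skin improved and no organ progressed. CR+PR is unchanged; the separate CR and PR rates (Table 14.2.2.4) are wrong by one each.

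**Which repair catches which patient.** A no-progression clause on CR removes the two large rises and leaves the two small ones as CR. Requiring liver score 0 at the visit as well removes all four.

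**Size of one patient.** Analyses b and d repeat SAP 11.4.1.1, a two-sided 95% Clopper-Pearson interval against 60%. I read its criterion as a lower limit above 60%; the sentence there has the direction reversed. Lower limit = 0.025 quantile of Beta(x, n - x + 1).

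- n = 24: 19 responders give 57.8%, 20 give 62.6%. One patient is 1/24 = 4.2 points.
- n = 21: 17 responders give 58.1%, 18 give 63.7%. One patient is 1/21 = 4.8 points.

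The actual denominator is the FAS (SAP 11.1), which requires a completed first cycle and a Week 6 evaluation. Analysis d also drops three named patients, so 24 - 3 = 21 if all 24 were in the FAS.

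**The case against.** The best defence is that 17.1 is a set of terse programming notes. Its header wants every listed organ at 0 and the liver is listed. The V1 condition follows the liver row of Protocol Table 4, where CR means normal values after an earlier elevation. The lung line, read equally literally, would refuse CR to a patient with normal lungs at V1, so a sensible programmer may not have coded every line to the letter. This stands as a caution about what was programmed. It does not rescue the text: Form A (Protocol Appendix 8) records liver laboratory values and no 0 to 3 liver score, so the liver line is the only workable rule, and nothing in 17.1 settles CR against PD.

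Several stronger readings are tempting and are not supported.

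- *The primary result is biased.* SAP 11.4.1.1 uses the investigator's response, not the algorithm.
- *A large liver rise is computed as a clean CR.* It is flagged CR and global PD together; counting it as a responder is one of two possible outcomes.
- *One patient crosses the line at 18 to 19 of 24.* That holds for an exact one-sided test of 60% (p = 0.096 and 0.040), which is not the criterion in 11.4.1.1. Under the interval the crossing is 19 to 20.
- *The case must be common, because Protocol 11.8 lists liver abnormalities among frequent events.* Those are drug toxicity, not new liver GvHD, and the non-GvHD flag properly removes them.
- *Bilirubin is left out of the CR test.* The text names all three values; the absent variable line is at most a listing slip.
- *A missing organ passes as no progression under PR.* This is secondary, since SAP 12.4.3.2 sends missing M6 assessments to data review.

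**Conclusion.** The point holds for the computed response. As written, 17.1 gives CR alone for new liver involvement with a rise of 2 x ULN or less, and CR with global PD for a larger one. Both conflict with the CR definition in SAP 8.2.1, and the second also with the protocol's mixed response.

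The reach is limited to sensitivity analyses b and d and their tables, and to consistency with PFS. Only the larger rises can change CR+PR; smaller ones shift a patient from PR to CR. One patient is 4 to 5 percentage points and can decide the interval criterion near 19/24 or 17/21.

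This assumes a literal reading of 17.1, a patient clear in every other organ at M6, and no non-GvHD attribution. The documents do not say how often this would occur, and no rate is claimed.

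**What to change.** Change SAP 17.1 in two places; both are needed.

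1. **Liver under CR.** Keep the three-value ULN test for livers involved at V1. Add that, for livers not involved at V1, global CR requires a liver score of 0 at the visit or the non-GvHD flag. The score must not replace the ULN test, because score 0 allows ALT and AP up to 3 x ULN: a V1-involved liver falling from ALT 6 to 2.9 x ULN would then pass as CR. Use the 11.2.3 derivation of the score; score 1 in 17.1 needs ALT and AP both raised and leaves some patients unscored.
2. **Progression.** Global CR requires no organ in progression, any organ progression excludes both CR and PR, and mixed response returns to CR or PR plus progression, as in Protocol 9.3.

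As a tidy-up, list the bilirubin variable beside SGPT and ALK.

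The cost is appendix wording and reprogramming one derived variable. No new data are needed, since Form A already records the liver values. The computed response rate may come out slightly lower.

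### SAP 17.1 states a three-value rule for liver complete response, but the variable conditions printed under it leave out bilirubin

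*SAP*

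**What the plan says.** SAP 17.1 gives the liver CR rule twice in words. Under complete response, for a liver score above 0 at V1, the requirement is "les 3 valeurs (Bilirubine, ALAT et PAL) sont en dessous des ULN". Under response by organ, the entry begins "pour Liver, (Bilirubine, ALAT ou PAL" and then says "si les valeurs à M6 sont en dessous des normales, la réponse est considérée Complète". The response table in SAP 8.2.1 puts the same requirement as "Normal ALT, alkaline phosphatase, and Total bilirubin after previous elevation of 1 or more". Table 4 of the protocol (section 7.3.2.1) and its reprint in SAP 17.1 carry the same entry.

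The conditions printed directly under the first sentence are:

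- "<M6_GVHD_A_L_SGPT_V<=M6_GVHD_A_L_SGPT_U_V", for ALT
- "<M6_GVHD_A_L_ALK_V<=M6_GVHD_A_L_ALK_U_V", for AP
- the variable that flags an abnormality explained by a cause other than GvHD

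Both comparisons are preceded by a full stop. In SAS, which the SAP names as its software, the full stop and the less-than sign together test that the value is not missing. No matching condition for bilirubin at the visit is printed. The V1 liver score a few lines lower does use a bilirubin variable: "<V1_GVHD_A_L_BILI_V<=V1_GVHD_A_L_BILI_U_V et".

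**The concern.** A programmer who works from the variable conditions would implement a two-value rule where the text states a three-value one. The error has one direction: it can only add liver CRs.

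Bilirubin is not a minor component. In the V1 scoring of SAP 17.1, raised bilirubin alone is enough for score 2 or 3, and score 3 depends on bilirubin only.

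The computed response also has a specific job. The main analysis in SAP 11.4.1.1 uses the investigator's judgement in a non-randomized study where blinding does not apply, and the computed response is the rule-based check on that judgement. A specification error that favours response weakens the check.

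**Working it through.** The documents give no figure on this point, so there is none to reproduce. The check is one of logic.

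**Inputs**

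- Rule in words (SAP 17.1 and the response table): liver CR if bilirubin, ALT and AP are all normal at the visit, given a V1 liver score above 0.
- Printed conditions (SAP 17.1): ALT not missing and ≤ ULN; AP not missing and ≤ ULN.
- Liver PR (SAP 17.1), read as (M6 − V1)/V1 × 100 below −50.
- Liver progression (SAP 17.1): M6 − V1 above 2 × ULN for any of the three values.

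**Step 1: all normal/raised combinations at the visit, liver involved at V1**

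| Bilirubin | ALT | AP | Printed conditions | Rule in words |
|---|---|---|---|---|
| normal | normal | normal | CR | CR |
| normal | normal | raised | no CR | no CR |
| normal | raised | normal | no CR | no CR |
| normal | raised | raised | no CR | no CR |
| **raised** | **normal** | **normal** | **CR** | **no CR** |
| raised | normal | raised | no CR | no CR |
| raised | raised | normal | no CR | no CR |
| raised | raised | raised | no CR | no CR |

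The two agree in 7 of 8 combinations. With a third condition for bilirubin they agree in 8 of 8.

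**Step 2: missing bilirubin.** The not-missing test is part of each printed comparison. With no bilirubin comparison, a missing bilirubin also passes as CR when ALT and AP are normal. That conflicts with the statement earlier in SAP 17.1 that a missing value in an organ involved at V1 rules out a complete response.

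**Step 3: illustrations** (assumed values; ALT and AP normal at the visit)

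| Bilirubin, V1 to M6 | Change | Difference | Rule in words | Printed conditions |
|---|---|---|---|---|
| 2.0 to 1.8 × ULN | (1.8 − 2.0)/2.0 = −10% | −0.2 × ULN | unchanged | CR |
| 2.5 to 4.0 mg/dL, ULN assumed 1.0 | (4.0 − 2.5)/2.5 = +60% | 1.5, below 2 × 1.0 | unchanged, although the liver score goes from 2 to 3 | CR |
| 1.5 to 4.0 × ULN | (4.0 − 1.5)/1.5 = +167% | 2.5 × ULN, above 2 | progression | CR conditions met, and progression met as well |

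In the last row the same liver meets two incompatible definitions.

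**Step 4: effect on the reported rates.** Suppose the other organs are at 0, so that the extra liver CR would make a global CR. An organ involved at V1 that has since fallen to 0 has usually met its own PR criterion. Under the rule in words that patient is then already a global PR, provided nothing has progressed. Bilirubin that has fallen by more than half but is still above ULN gives a liver PR with the same result. In these cases only the split between CR and PR moves. The combined CR+PR rate moves only when no other organ responds and bilirubin has not met the PR criterion. One such patient is 1/24 = 4.2 percentage points or 1/21 = 4.8 percentage points, if the analysis set has the planned 24 or the required 21 patients. The actual size of the full analysis set is not known from the documents.

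**Step 5: what is not touched.** The design rule of 17 or more responders out of 21 has exact alpha 0.0370 at 60% and power 0.8025 at 85%, and 21/(1 − 0.10) = 23.3 rounds up to 24. These match the plan and involve no liver term. Progression in SAP 17.1, which SAP 11.4.2.2 uses for progression-free survival, names bilirubin explicitly.

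**The case against.** The strongest reply is that the rule itself is right and is stated more than once, the first time in the line directly above the conditions. On this view the lines under each organ are pointers to database fields. For skin, eyes, gastrointestinal tract, mouth and joints they are bare variable names with no test. For lung, the V1 FEV1 requirement in the prose has no variable listed. A program written from the prose would be correct.

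Much of this stands. No program is in the documents, so the text does not show that any patient with raised bilirubin has been classed as a liver CR. It is also possible that a line was lost when the PDF was read: the V1 block prints bilirubin, ALT and AP in that order, and the visit block shows only the last two.

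It does not remove the point. Unlike the bare names, the liver lines carry comparison operators and missing-value tests, so they read as conditions to be coded. The other organs with several components list them all: skin 2 of 2, gastrointestinal 3 of 3, mouth 3 of 3. Liver announces three and lists two.

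A reader might also infer that every patient with isolated raised bilirubin at V1 counts as CR whatever bilirubin then does. The documents do not support that. ALT and AP must be normal at the visit, and the progression rule still applies to bilirubin. Nor is bilirubin the only route to the more severe scores: score 2 is also reached by ALT or AP at 5 × ULN or more.

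**Conclusion.** The inconsistency is real and should be removed. As printed, the liver CR conditions in SAP 17.1 do not implement the rule that the same section and the response table state. The misclassification is conditional: it occurs only if the program follows the printed conditions alone, and only for a liver involved at V1 with ALT and AP normal and bilirubin raised or missing at the visit.

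The reach is narrow. It covers sensitivity analyses b and d of SAP 11.4.1.2, with their separate CR and PR proportions, and the liver row of the table in 11.4.2.1. The usual effect is a shift from PR to CR. A change of 4.2 to 4.8 percentage points in the combined rate is the effect of one patient who has no other qualifying response, under the assumed denominators. The documents do not say how many such patients there are, if any.

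A reader might infer that the primary result is biased. It is not affected by this: SAP 11.4.1.1 takes the response as judged by the investigator.

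**What to change.** In SAP 17.1, add `.<M6_GVHD_A_L_BILI_V<=M6_GVHD_A_L_BILI_U_V` to the liver CR conditions, with the same line under the prefixes C1W6, W14, M9 and M12. Keep the leading not-missing test, so that a missing bilirubin cannot pass. Then check the program against the three-value rule, and check the source SAP to see whether the line is absent there or was lost in conversion.

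The cost is one condition per visit in the specification and, if needed, in the program. No new data are required, because bilirubin and its ULN are recorded on Form A (protocol Appendix 8). No sample size, power or primary analysis changes.
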